#### **Detailed Description:**

Diagnostic errors represent a significant cause of preventable patient harm in healthcare systems worldwide. Recent advances in Large Language Models (LLMs) have shown promise in enhancing medical decision-making processes. However, there remains a critical gap in our understanding of how automation bias -- the tendency to over-rely on technological suggestions -- influences medical doctors' diagnostic reasoning when incorporating these AI tools into clinical practice.

Automation bias presents substantial risks in clinical environments, particularly as AI tools become more integrated into healthcare workflows. Although LLMs such as ChatGPT-40 offer potential advantages in reducing errors and improving efficiency, their lack of rigorous medical validation raises concerns about potentially amplifying cognitive biases through the generation of incorrect or misleading information.

Multiple contextual factors can exacerbate automation bias in medical settings: time constraints in highvolume clinical settings, financial incentives that prioritize efficiency over thoroughness, cognitive fatigue during extended shifts, and diminished vigilance when confronting diagnostically challenging cases. These factors may interact with psychological mechanisms that include the diffusion of responsibility, overconfidence in technological solutions, and cognitive offloading---collectively increasing the risk of uncritical acceptance of AI-generated recommendations.

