This randomized controlled trial (RCT) aims to systematically measure the extent and patterns of automation bias among physicians when utilizing ChatGPT-40 in clinical decision-making. The investigators will assess how access to LLM-generated information influences diagnostic reasoning through a novel methodology that precisely quantifies automation bias. In this study, participants will be randomly assigned to one of two groups. The treatment group will receive LLM-generated recommendations containing deliberately introduced errors in a subset of cases, while the control group will receive LLM-generated recommendations without such deliberately introduced errors. Participants will evaluate six clinical vignettes randomly sequenced to prevent detection patterns. The flawed vignettes provided to the treatment group will incorporate subtle yet clinically significant errors that should be identifiable by trained doctors. This will enable investigators to quantify the degree of automation bias by measuring the differential in diagnostic accuracy scores between the treatment and control groups.

Prior to participation, all physicians will complete a comprehensive training program covering LLM capabilities, prompt engineering techniques, and output evaluation strategies. Responses will be evaluated by blinded reviewers using a validated assessment rubric specifically designed to detect uncritical acceptance of erroneous information, with greater score disparities indicating stronger automation bias. This naturalistic approach will yield insights directly applicable to real clinical workflows, where mounting cognitive demands may progressively impact diagnostic decision quality.

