#### **Power Analysis:**

The minimum target sample size of 50 participants (25 participants per arm) was predetermined based on a prior study. The power analysis, conducted using Python version 3.11.9 (Python Software Foundation), employed the statsmodels.stats.power module from statsmodels version 0.14.4 (Statsmodels Developers) and indicated that a total sample of 200 to 250 completed cases (approximately 4 to 5 cases per participant) would provide at least 80% power to detect an 8-percentage-point mean difference in diagnostic reasoning scores, assuming a two-sided  $\alpha$  of .05. The analysis employed mixed-effects models suitable for cluster-randomized designs, considering an intraclass correlation coefficient (ICC) ranging from 0.05 to 0.15 and a standard deviation of 16.2%.

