A secondary analysis will be conducted to measure the sequential trend in automation bias. A linear mixedeffects model will be used, with random intercepts for participants and for vignettes, and fixed effects for vignette order, treatment arm, and their interaction. The dependent variable will be the vignette-level diagnostic reasoning performance (percentage); the sequence-by-treatment interaction will then quantify how the treatment arm's trajectory deviates from control, reflecting any progressive automation bias across successive vignettes. We will repeat this analysis for the secondary outcome as well.

Subgroup analyses will be performed based on experience with LLMs, gender and years of practice post MBBS. Scores for each case question will also be compared descriptively between the two randomized groups.

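### The sequential-trend model has random intercepts only, so if physicians differ in their trend over the session, the order-by-arm interaction gets too small a standard error

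*Combined protocol and SAP*

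**What the plan says.** The Statistical Analysis section plans a secondary analysis of trend across the session. The outcome is the vignette-level percentage score, and the model is a linear mixed model "with random intercepts for participants and for vignettes, and fixed effects for vignette order, treatment arm, and their interaction". The result is read as follows: "the sequence-by-treatment interaction will then quantify how the treatment arm's trajectory deviates from control, reflecting any progressive automation bias across successive vignettes". It then adds: "We will repeat this analysis for the secondary outcome as well".

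The section gives no participant random slope for order, no cluster-robust standard error and no sensitivity analysis for this model. Its numbered list of sensitivity analyses follows the primary analysis. Clustering by participant is also mentioned there, where it means a participant random effect.

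On design, the Detailed Description says: "Participants will evaluate six clinical vignettes randomly sequenced to prevent detection patterns". The Power Analysis section says: "The minimum target sample size of 50 participants (25 participants per arm) was predetermined based on a prior study". Its calculation rests on "a total sample of 200 to 250 completed cases (approximately 4 to 5 cases per participant"), and concerns the overall arm difference only. No power, effect size or slope SD is given for the trend.

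**The concern.** Order varies within a physician and arm varies between physicians. The order-by-arm interaction is therefore a difference between two average within-physician slopes, 25 in each arm. If physicians in the same arm change at different rates, that variation is part of the sampling error of each average. An intercept-only model has no term for it and treats most of it as independent case-level noise.

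The error then runs in one direction: an interval that is too narrow and a p value that is too small. This interaction is the test on which the plan would base a statement about progressive automation bias, and it is to be repeated for the secondary outcome.

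**Working it through.** **Inputs from the documents.** SD 16.2; ICC 0.05 to 0.15; two-sided alpha 0.05; 25 participants per arm; six vignettes in random order; 4 to 5 completed cases per participant in the power calculation.

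**Assumptions.** The between-physician slope SD, τ, is not in the documents; it is set at 0, 1, 2 and 3 points per position. ICC is 0.10 unless stated. Variance not due to participants is taken as case-level residual. With m completed cases, positions are taken as 1 to m.

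**Step 1: the plan's own figure.** The section states that the sample "would provide at least 80% power to detect an 8-percentage-point mean difference in diagnostic reasoning scores". The effective number of cases per arm is (cases/2)/(1 + (m − 1) × ICC).
- 200 cases, m = 4, ICC 0.15: 100/1.45 = 68.97; SE = 16.2 × √(2/68.97) = 2.759; power 82.6%. At ICC 0.05, 90.3%.
- 250 cases, m = 5: 87.0% (ICC 0.15) to 94.6% (ICC 0.05).

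The statement reproduces, but it says nothing about the trend test.

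**Step 2: the two variances.** Let σ² = 16.2² × 0.90 = 236.2, and let S be the centred sum of squares of position: 17.5 for six cases, 10 for five, 5 for four.
- Actual variance of the interaction: (2/25) × (σ²/S + τ²).
- Variance reported by the intercept-only model: (2/25) × (σ² + τ² × S/(m − 1))/S.

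Only 1/(m − 1) of the slope variance reaches the reported variance, which is one fifth with six cases.

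**Step 3: a worked case.** Six cases, τ = 2:
- Actual SE = √[0.08 × (236.2/17.5 + 4)] = 1.183.
- Reported SE = √[0.08 × (236.2 + 14)/17.5] = 1.069.
- Ratio 1.183/1.069 = 1.11.
- Type I error = 2 × [1 − Φ(1.96/1.106)] = 7.6%.

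**Step 4: all settings** (ratio of actual to reported SE; type I error).

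| Completed cases | τ = 0 | τ = 1 | τ = 2 | τ = 3 |
|---|---|---|---|---|
| 6 | 1.00; 5.0% | 1.03; 5.7% | 1.11; 7.6% | 1.21; 10.6% |
| 5 | 1.00; 5.0% | 1.02; 5.4% | 1.06; 6.4% | 1.12; 8.1% |
| 4 | 1.00; 5.0% | 1.01; 5.2% | 1.03; 5.6% | 1.06; 6.4% |

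The ICC matters little: with six cases and τ = 3, the type I error is 10.3% at ICC 0.05 and 10.9% at ICC 0.15.

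**Step 5: simulation checks, six cases.**
- 20,000 runs of the intercept-only test gave 5.2%, 5.9%, 7.4% and 11.0% for τ = 0, 1, 2 and 3. A t-test on per-participant slopes, which allows slopes to differ, gave 4.7% to 5.2%.
- Fitted random-intercept REML models (1,500 runs) gave 7.7% at τ = 2 and 10.8% at τ = 3.
- A smaller fitted check (400 runs, τ = 3) gave a milder 7.5% for random intercepts and 4.3% with a random slope. Its Monte Carlo standard error is about √(0.075 × 0.925/400) = 1.3 percentage points.

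**The case against.** **The deciding quantity is not in the documents.** A reader might infer from the background on "cognitive fatigue during extended shifts, and diminished vigilance when confronting diagnostically challenging cases" that the plan itself implies differing trajectories. It does not. That text lists general factors in medical settings, and the trend analysis describes an average change. An average trend is a fixed effect and can exist with τ = 0, where the planned model holds 5%. This objection stands: the point is conditional.

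**The larger τ values are demanding.** At ICC 0.10, physicians differ in level with an SD of 16.2 × √0.10 = 5.1 points. Over the five steps from first to sixth vignette, τ = 2 means that change varies with an SD of 10 points, and τ = 3 with an SD of 15. At τ = 1 the SD of change is 5 points, similar to the level SD, and the inflation is negligible. On the other hand, τ = 2 and 3 make up only about 6% and 12% of within-physician variance (14/250.2 and 31.5/267.7), so they cannot be ruled out.

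**Fewer completed cases shrink the problem.** At the four cases in the power calculation, the type I error is at most 6.4% over this range. This also stands.

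**It is not gross pseudoreplication.** A reader might infer that the model treats about 300 cases (50 × 6) as independent. It does not: it has a participant intercept, and the standard error is short by a factor of 1.21 at most over the range shown.

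**The repeat for the secondary outcome was not checked.** That outcome is analysed elsewhere in the section with an ordinal mixed model, and every figure here is for a continuous score. No size can be claimed for it.

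**A sparse model is partly a matter of judgement.** With at most six points per person, a slope term costs some precision when τ is near zero and may not converge. A short check of random-slope fits met many convergence warnings. This bears on how the fix is written and does not remove the point.

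**Conclusion.** The point holds in conditional form. If physicians differ in their trend over the session, the planned intercept-only model understates the standard error of the order-by-arm interaction, and nothing else in the plan corrects this. Over assumed slope SDs of 1 to 3 points per position, the type I error is 5.7% to 10.6% with six completed cases, 5.4% to 8.1% with five and 5.2% to 6.4% with four. It is materially inflated only when both slope variation and completion are high.

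These figures rest on SD 16.2, ICC 0.10, 25 per arm, a continuous score and slope SDs that are assumptions. The documents do not support saying that the trial's trend result will be wrong. This is a secondary analysis, and the primary arm comparison is unaffected. The change is still worth making, because it is cheap and protects the only test of a progressive effect.

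**What to change.** In the sequential-trend paragraph of the Statistical Analysis section:

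1. Add a participant random slope for vignette order, uncorrelated with the intercept, to the linear model for the percentage score.
2. Name one fallback if that model does not converge: participant-clustered small-sample (CR2) standard errors. A single named fallback avoids choosing the test after seeing the data.
3. Treat the secondary outcome separately. Use the same participant slope, or participant-clustered errors, where the ordinal model allows it, and state that the size of the problem was not calculated for an ordinal outcome.
4. The Study Design section lists actual completion dates. If the analysis has already been run, report the revised model as a sensitivity analysis, label it as such, and base any statement about progressive automation bias on it.

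The cost is a few lines of text and no new data. The interval becomes slightly wider: with six cases and τ = 2, the standard error is 1.18 against 1.07 points per position. Non-convergence is a real possibility with at most six cases per physician, so the fallback may be used often.

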#### Arms and Interventions

Arm	Intervention/Treatment
Active Comparator: ChatGPT-40	Other: ChatGPT-40 Recommendations with
Recommendations with Hallucinations	Hallucinations
Participants will evaluate six clinical vignettes.	
During the trial, they will have access to clinical	ChatGPT-40's differential diagnoses of six clinical
recommendations from a specific, commercially	vignettes, three of which will contain deliberately
available LLM (ChatGPT-40) in addition to	introduced inaccurate information.
conventional diagnostic resources. LLM	*
recommendations for three vignettes will contain	
deliberately flawed diagnostic information and for	
three vignettes it will contain accurate	
recommendations). The cases will be presented in	
random order.	
No Intervention: ChatGPT-40 Recommendations	
without Hallucinations	
Participants will evaluate the same six clinical	
vignettes as in the intervention arm. During the	
trial, they will have access to clinical	
recommendations from a specific, commercially	
available LLM (ChatGPT-40) in addition to	
conventional diagnostic resources. However, the	
LLM-generated recommendations will not contain	
any deliberately introduced errors. The cases will	
be presented in random order.	

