#### Exploratory Analyses

- Within-subject difference in diagnostic reasoning score between the 3 clinical vignettes without flawed LLM recommendations and 3 vignettes with flawed LLM recommendations and the corresponding difference in vignettes in the control group.
- Standalone LLM Performance: The standalone performance of the LLM will be compared to the control group using an independent samples t-test

Missing data patterns and extent will be described for all variables. The primary analysis will follow an intention-to-treat framework using complete case analysis. If substantial missing data occurs (>5% for any key variable), multiple imputation will be implemented and results compared with the complete case approach to assess robustness of findings. Given the small sample size, no interim analyses are planned.

All statistical analyses will be performed using Python software, version 3.11.12 (Python Software Foundation) with pandas for data manipulation and statsmodels version 0.14.4 for mixed-effects modeling, R (version 4.3.2 or later) or similar packages. Statistical significance will be based on a p value.

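### The order-by-arm interaction averages the trend over all six vignettes and cannot by itself show progressive automation bias, because only three are flawed and the model has no term for flaw status

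*Combined protocol and SAP*

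**What the plan says.** The trend analysis in the Statistical Analysis section uses random intercepts for participant and vignette, with "fixed effects for vignette order, treatment arm, and their interaction". It is fitted to vignette-level percentage scores and is repeated for the secondary outcome. No restriction to flawed vignettes is stated and there is no term for flaw status. The plan's reading of the result is that "the sequence-by-treatment interaction will then quantify how the treatment arm's trajectory deviates from control, reflecting any progressive automation bias across successive vignettes".

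The Arms and Interventions table describes the treatment arm's advice as covering six vignettes, "three of which will contain deliberately" introduced errors. The other three have accurate advice, and the control arm has no deliberate errors. The Detailed Description has "six clinical vignettes randomly sequenced to prevent detection patterns", without saying whether each participant gets a separate order. It measures automation bias by "measuring the differential in diagnostic accuracy scores between the treatment and control groups", and describes the scoring rubric as "specifically designed to detect uncritical acceptance of erroneous information, with greater score disparities indicating stronger automation bias".

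The one planned contrast by flaw status is under Exploratory Analyses: "Within-subject difference in diagnostic reasoning score between the 3 clinical vignettes without flawed LLM recommendations and 3 vignettes with flawed LLM recommendations", set against the same difference in controls. It has no order term.

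**The concern.** The interaction describes how the gap between arms changes with position, averaged over flawed and accurate vignettes. Progressive automation bias is a narrower claim: that physicians increasingly accept wrong advice as they go on. Only the flawed vignettes can show that.

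A treatment-arm decline on accurate vignettes could have the opposite cause. Physicians who have noticed errors may begin to disregard advice that is correct. Their scores then fall on accurate vignettes, the interaction is negative, and the plan's sentence would report it as growing automation bias. Conversely, a real trend confined to flawed vignettes appears at half its size, and opposite trends on the two types cancel.

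**Working it through.** **Inputs from the documents.** 25 participants per arm, SD 16.2, ICC 0.05 to 0.15, two-sided 5% (Power Analysis); six vignettes, three flawed (Arms and Interventions).

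**Assumed, because the documents give no values.** Order randomised per participant; controls flat over order; mean effect of -8 on flawed cases; treatment-minus-control slopes in points per position. A slope of -4 is large (4 x 5 = 20 points from first to last); -2 is modest. ICC is 0.10 unless stated.

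**1. The plan's own power figure.** It concerns the arm main effect: at least 80% for 8 points with "a total sample of 200 to 250 completed cases (approximately 4 to 5 cases per participant". The effective number per arm is (cases/2)/(1 + (m - 1) x ICC).
- 200 cases, m = 4, ICC 0.15: 100/1.45 = 69.0; SE = 16.2 x sqrt(2/69.0) = 2.76; 8/2.76 = 2.90; power 82.6%. At ICC 0.05 it is 90.3%.
- 250 cases, m = 5: 87.0% and 94.6%.

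The figure reproduces. No power is stated for the order-by-arm interaction.

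**2. What the interaction estimates.** Let sF and sA be the arm differences in slope on flawed and accurate vignettes. With individually random order, each position holds a flawed vignette with probability 3/6. The expected arm difference at position k therefore has slope (sF + sA)/2, whatever the constant flaw effect.
- sF = -4, sA = 0: -2
- sF = 0, sA = -4: -2
- sF = sA = -2: -2
- sF = -4, sA = +4: 0

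**3. Standard errors.** Residual variance is 0.90 x 16.2^2 = 236.2. The sum of squares of positions 1 to 6 about 3.5 is 17.5. So SE is about sqrt(2 x 236.2/(25 x 17.5)) = 1.04. Simulation by generalised least squares, with vignette effects fitted as fixed, gives 1.07. Half the cases gives about sqrt(2) x 1.07 = 1.51 for the flawed slope; simulation gives 1.52. The flawed-minus-accurate difference in slopes has SE 2.20.

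**4. Rejection rates, all 300 cases** (1,500 simulated trials per row, so within about 3 points). As a check on the first row, the normal approximation Phi(|slope|/SE - 1.96) gives Phi(2.0/1.07 - 1.96) = 46% and Phi(4.0/1.52 - 1.96) = 75%.

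| sF / sA | Pooled coefficient | Pooled test rejects | Flawed-slope test rejects |
|---|---|---|---|
| -4 / 0 | -2.0 | 48% | 75% |
| -2 / 0 | -1.0 | 17% | 26% |
| 0 / -4 | -2.0 | 44% | 5% |
| -4 / +4 | 0.0 | 5% | 75% |
| -4 / -2 | -3.0 | 81% | 76% |
| -4 / -4 | -4.0 | 96% | 76% |
| -2 / -2 | -2.0 | 46% | 24% |
| 0 / 0 | 0.0 | 5% | 4% |

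For -4 / 0, ICC 0.05 to 0.15 gives 46-50% and 73-79%. A different estimator (two-way centring on participant and vignette) gives 42% and 71%, with the same coefficients to within 0.1.

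**5. Break-even.** With sA = r x sF, the two tests have equal power when (1 + r)/(2 x 1.07) = 1/1.52, so r = 2 x 1.07/1.52 - 1 = 0.41. Above that, pooling has more power.

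**6. Slope needed for 80% power (2.8 x SE).** Pooled: 2.8 x 1.07 = 3.0. Flawed: 2.8 x 1.52 = 4.3.

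**7. Four or five cases per participant, -4 / 0.** If only the first 4 or 5 are completed: 16-30% pooled and 30-52% flawed. If a random 4 or 5 are completed: 34-40% and 55-66%.

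**8. If one order were shared by everyone.** A constant flaw effect would then look like a trend. With the flawed vignettes at positions 4 to 6, a constant -16 gives -16 x (0.5 + 1.5 + 2.5)/17.5 = -4.11 per position. At positions 1 to 3 it gives +4.11.

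**The case against.** **The exploratory contrast may already separate the explanations.** The simulation centres order, so a slope of -4 with a mean of -8 implies that flawed advice helps by 2 points at position 1 (-8 + 2.5 x 4). Similarly, the accurate-only scenario starts 10 points above control, before any flawed case has been seen. If divergence starts at position 1 instead, with a constant flaw effect of -8, the exploratory contrast has expectation -8 - 10 = -18 for flawed-only decline and -8 + 10 = +2 for accurate-only decline. They lie 20 points apart, with an SE of about 3.6. The criticism of the parameterisation is fair, but it leaves the interaction unchanged. The separation also depends on knowing the constant flaw effect. Flawed-only decline with constant 0 gives 0 - 10 = -10; accurate-only decline with constant -20 gives -20 + 10 = -10. A contrast of levels cannot identify a slope. The planned descriptive comparison of question scores between arms does not include order either.

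**The interaction follows the plan's own measure.** The document's definition is over-reliance on technological suggestions, its measure is the arm differential, and the phrase about accepting erroneous information describes the rubric. This stands as a defence of the model, which is why the pooled term should be kept. It does not rescue the interpretation: disregarding correct advice is not over-reliance either, yet it moves the coefficient in the same direction.

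**The sizes are assumed and the benefit is limited.** This stands. A slope of -4 totals 20 points, 2.5 times the design difference of 8. At -2 neither test has useful power, and shared trends favour the planned model. An effect of -8 on flawed cases alone is also only -4 on the pooled arm difference. The loss of power is therefore conditional; the lack of specificity is not.

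**Conclusion.** The concern holds. The interaction is a valid average arm-level trend provided order was randomised per participant, which the documents do not state. It is not specific to progressive automation bias: flawed-only -4, accurate-only -4 and -2 on both all give about -2.0, and no planned analysis tells them apart. That conclusion follows from three of six vignettes being flawed and needs no assumed slope. The power figures do depend on the assumed slopes, ICC and completion.

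What is at stake is the wording and support of one secondary conclusion on the trial's central construct. The primary comparison is unaffected.

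**What to change.** - Keep the pre-specified pooled interaction and describe it only as the average arm-level trend over all six vignettes.
- Add flaw status (in controls, the counterpart vignettes) with its arm and order interactions. Report the arm-by-order slope on flawed vignettes and the one on accurate vignettes, each with a confidence interval.
- Rest any claim of progressive automation bias on the flawed-vignette slope.
- State whether order was randomised separately for each participant.
- Do the same for the secondary outcome with the ordinal model, where the one-half relation is only approximate.

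The cost is a few terms in a planned model and no new data. The flawed slope is less precise (SE about 1.5 against 1.07), power for modest slopes is low either way, and incomplete cases lower it further. Because the flawed-minus-accurate difference has SE 2.2, failure to find one should not be read as equal trends. Study Design gives actual completion in July 2025, so if data have been seen the added slopes should be reported as supplementary and post hoc.
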